2.2.7.3 Sudden Cardiac Death

Time to event for sudden cardiac death will be analyzed using the same methodology described for the primary outcome at a 0.05 2-sided significance level. VA Vital Status File will be used to determine the vital status of all study participants who are lost to follow-up at study exit. VA Vital Status File search plus a NDI Plus database search for all participants who are found to have died through the VA database search will be performed in order to adjudicate the cause of death (Table 23).

2.2.7.4 Informed Consent Questionnaire

Additionally, data from the Informed Consent Questionnaire will be used for exploratory analysis of the association between perceived and actual participant understanding of the study. The goal of this analysis is to measure which study nuances are most easily understood. The first part (Items 1-11) of Informed Consent Questionnaire measures the patients' perception/knowledge of the study. The total number and proportion of correct responses per each item will be calculated for each subject. Mean and standard deviation will be calculated for each group.

The second part (Question 12-15) comprises validated items that measures patients' perceived understanding of the study³⁵, which are subjective patients' reports of their own understanding. The perceived understanding is scored on 0 to 3 scales with total

score of 0 to 9. Higher scores indicate greater perceived understanding. The association between perceived and actual participant understanding of the study can be measured by agreement analysis between part 1 and part 2. In addition, the association between patients' perceived understanding and the probability of patients' withdrawal and other factors in baseline, such as patients' age will also be studied. We note that because these data are collected during the consenting procedure, there is no plan to analyze by treatment group.

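### SAP 2.2.7.4 gives the four perceived-understanding items a total range that fits only three, and names an agreement analysis for an association between scores on different scales

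*Combined protocol and SAP*

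**What the plan says.** SAP section 2.2.7.4 splits the Informed Consent Questionnaire into two parts.

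- Part 1: "The first part (Items 1-11) of Informed Consent Questionnaire measures the patients' perception/knowledge of the study". It is summarised by the number and proportion of correct responses.
- Part 2: "The second part (Question 12-15) comprises validated items that measures patients' perceived understanding of the study". Its scoring rule reads "The perceived understanding is scored on 0 to 3 scales with total" and continues "score of 0 to 9. Higher scores indicate greater perceived understanding".

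On relating the two, the SAP says: "The association between perceived and actual participant understanding of the study can be measured by agreement analysis between part 1 and part 2". It names no statistic, common scale or cut-points. It also plans to relate perceived understanding to withdrawal and to baseline factors such as age.

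Protocol section XV.C.6 speaks only of an exploratory analysis of the association between perceived and actual understanding. The SAP adds that no analysis by treatment group is planned.

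**The concern.** Two things in this short section do not fit together.

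First, the item numbering, the item scale and the total range cannot all be right. Whoever programs the score must either sum four items and exceed the stated range, or leave one out and decide which. Neither choice is documented.

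Second, the question is one of association: do participants who know more also feel that they understand more? Agreement is a different property. It asks whether two measurements of the same quantity give the same value, which presupposes a common scale. Part 1 counts correct answers and part 2 totals self-ratings, so their raw values need not match even when they rank participants identically.

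At stake are the definition of the perceived-understanding score, which the withdrawal and age analyses also use, and the interpretation of the planned coefficient.

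**Working it through.** **Inputs, all from SAP 2.2.7.4**

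- Part 2 items: Questions 12 to 15, so 15 − 12 + 1 = 4.
- Part 2 item scale: 0 to 3.
- Stated part 2 total: 0 to 9.
- Part 1 items: 1 to 11, so 11. The count runs 0 to 11 if each item earns one point (an assumption; the SAP does not say). The proportion runs 0 to 1.

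**Attempt to reproduce the stated total**

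For a simple sum, maximum = number of items × item maximum.

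- Four items on 0 to 3: 4 × 3 = 12. This does not reproduce 9.
- Three items on 0 to 3: 3 × 3 = 9. This matches the total but not the item numbering.
- Four items on 0 to 2: 4 × 2 = 8, a range of 0 to 8. No match.
- Four items on 1 to 4: 4 × 1 = 4 to 4 × 4 = 16. No match.
- Four items with a total of 9: item maximum 9 / 4 = 2.25, which is not the stated scale.

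As a simple sum, no reading keeps both four items and a 0-to-3 scale and gives 0 to 9.

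**Response patterns outside the stated range, if all four items are summed**

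There are 4⁴ = 256 possible patterns. A total above 9 means a shortfall of 0, 1 or 2 points from 12:

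- total 12: 1 pattern
- total 11: 4 patterns (one item scored 2)
- total 10: 10 patterns (4 with one item scored 1, and 6 with two items scored 2)

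The sum is 1 + 4 + 10 = 15, and 15 / 256 = 5.9%. This is a share of patterns, not a forecast of the share of participants. It includes the pattern of 3 on every item, the highest perceived understanding that can be recorded.

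**Agreement against association**

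Suppose the two parts are perfectly related, so that each participant reaches the same fraction of the maximum on both. Call the part 1 count x.

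- If part 2 runs 0 to 9, its total is (9/11)x. The raw difference is x − (9/11)x = (2/11)x, which is 2 points at x = 11.
- If part 2 runs 0 to 12, its total is (12/11)x. The raw difference is x − (12/11)x = −(1/11)x, which is −1 point at x = 11.
- If part 1 enters as a proportion and part 2 as a raw 0-to-9 total, a participant at the top of both has 1 against 9.
- If both are divided by their maximum, the difference is 0 for everyone.

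The correlation is 1 in every case. Only the raw disagreement changes, and its size and sign depend on the scale, including whether part 2 runs to 9 or to 12. The unresolved range therefore feeds into any raw-score agreement statistic.

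**The case against.** The strongest defence is that the scoring may be right and only the description loose. Part 2 is said to consist of validated items, with a citation. If the cited measure scores three of the four questions, 0 to 9 is correct and only the item list needs a note. Protocol VIII.B places the data forms in Appendix E, which is not in the text reviewed. This stands in part: a reader might infer that the derived score is wrong, and the documents do not support that. They show a contradiction, and the error could lie in the total, the item range, the item scale or the number of items scored.

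A second defence is that the SAP says only that the association "can be measured by agreement analysis between part 1 and part 2". That wording is permissive. It does not require raw scores, part 1 already yields a proportion, and agreement can be computed after rescaling or categorising. This also stands. A reader might infer that the planned association is invalid, but the text supports only that the method is unspecified and, on raw scores, ill-suited to the question.

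A reader might also object that correct responses tallied by item within each participant cannot show which points of the study are best understood, since each value is 0 or 1. The next sentence of the SAP calls for means and standard deviations, and the mean of a 0/1 item across participants is its proportion correct. That goal can be met as written.

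Finally, the impact is small. The analysis is exploratory in both documents, and the SAP's list of reporting tables has none for it. The questionnaire's main purpose, in protocol VII.C, is to check understanding during consent, which the score range does not affect.

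**Conclusion.** The point holds as an internal inconsistency and an under-specified method. Four items on a 0-to-3 scale give 0 to 12, 3 points above the stated maximum of 9; the stated range fits three scored items. The documents do not settle which is intended. The only assumption is that the total is a simple sum.

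The agreement analysis does not match the stated question unless the scores are first put on a common scale. Even then it asks whether the two fractions coincide, which is narrower than whether they rise together. No size can be put on the effect in this trial, because the documents give no distribution for either part. The worked differences show direction and mechanism only, and take one point per part 1 item.

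The consequence is limited to an exploratory, non-comparative analysis and to the associations with withdrawal and age. For those associations the choice of three or four items matters, but the stated maximum itself does not. The primary and secondary outcomes, safety analyses, interim monitoring and sample size are untouched. This is a modest clarification, worth making because the score cannot be programmed as written without an undocumented choice.

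**What to change.** Amend SAP 2.2.7.4 in two places.

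1. State which of Questions 12 to 15 enter the perceived-understanding total and give the matching range: 0 to 12 if all four are summed, 0 to 9 if three are. If three, name the unscored question and say how it will be reported. Check this against the questionnaire form and the cited measure.
2. Replace the agreement analysis with a Spearman rank correlation between each participant's part 1 proportion correct (over 11 items) and part 2 total. Ranks do not depend on either maximum, so the result is free of the scale difference. If agreement is itself of interest, put both parts on a common scale, or define categories for both, before naming the agreement statistic.

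Use the same defined total in the withdrawal and age analyses. The cost is a wording change, with no new data collection and no effect on trial conduct.

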2.2.8 Device Data

ICDs are capable of delivering information related to a wide range of parameters including activity level, heart rate variability, as well as data related to the delivery and cessation of arrhythmic therapy. The device data will be collected during study follow-up visits for participants in the ICD arm and followed by remote monitoring where possible. Descriptive analysis will be used to summarize the ICD device data. The analysis will be focused on three activities in particular:

- (1) Routine assessment of device activations to assess shock events. The shock events will be summarized and grouped in relevant categories, e.g. by year, by age, by health status, by cause, and by resolution/outcome, and whether appropriate or inappropriate shock³⁶. Subjects with no recorded events will also be noted.
- (2) The risk of death after shock will be analyzed for both appropriate shock and inappropriate shock
- (3) Analysis of device data at follow-up appointments as is done in standard clinical practice.

ICD therapy will be defined as either antitachycardia pacing (ATP) or ICD shock. Any ICD therapy not delivered for VT or VF will be deemed inappropriate, and the rhythm triggering therapy categorized as: atrial fibrillation or atrial flutter (AF), supraventricular including sinus tachycardia (SVT), or inappropriate sensing using published criteria. An episode's termination will be defined by the ICD re-detecting sinus rhythm and thus could include more than 1 shock (and/or ATP bursts). As done previously in the AVID (Antiarrhythmics Versus Implantable Defibrillators) study, a subsequent episode beginning <5 min after episode termination will be ignored for this analysis. Thus, an inappropriate shock episode will be defined as an episode during which one or more inappropriate shocks occurred; a separate ICD episode of the same type (inappropriate or appropriate) occurring <5 min later will not be counted.

Descriptive statistics will be used to summarize all clinical characteristics. The Kaplan-Meier life-table method will be used to graphically display the time to first shock event and calculate the cumulative event rates for each group. The results will be compared using the log-rank statistic.

Among the patients who have an active ICD, we will use a Cox regression to evaluate what factors are associated with time to inappropriate shock where time to the first inappropriate shock will serve as the dependent variable, and subjects who never experience a shock or experience only appropriate shocks will be censored at the last time of follow-up. In a similar way, we will evaluate the association of inappropriate, appropriate shock with mortality where time to death will serve as dependent variable and inappropriate shocks, appropriate shocks and other related clinical variables will be

included as time-dependent co-variates. These analyses may provide insights in understanding how the device shock therapies are utilized and affect the study outcomes.

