CSP #592 will enroll 1,462 total participants (an average of approximately 55 participants from each of the 27 participating sites). Patients who meet the standard profile of a candidate for ICD therapy according to current Centers for Medicare & Medicaid Services criteria for primary prevention and are at least 70 years of age will be screened for eligibility. CMS criteria primarily include patients with an established diagnosis of chronic heart failure, a qualifying ejection fraction, and survivability beyond 12 months. The primary exclusion criteria for the study are: 1) contemporaneous participation in an ongoing interventional clinical trial, 2) inability to complete study protocol, or 3) election into receiving a bi-ventricular ICD device. Details of the eligibility criteria are provided in Chapter V. The inclusion criteria were designed to include a broad sample of elderly patients eligible for an ICD with few exclusions, in order to maximize generalizability.

C. Treatments and Rationale

1. Overview

The primary goal of this study is to compare ICD on top of optimal medical therapy against optimal medical therapy alone in reducing overall mortality in the patients with advanced age. For those participants randomized to the ICD group, implantation will occur as soon as possible after enrollment, with a target of 1 week post-randomization. A thorough medical history will be recorded prior to randomization for all participants, and stability on optimal medical stability will be established before participant can be randomized. After randomization, all participants will be returned to clinical care for continuation of their optimal medical therapy, according to local standard care for heart failure patients. Study follow-up phone calls will be scheduled for months

1 to 4, and at 6-month intervals post-randomization (6 months, 12 months, 18 months, etc.), all conducted by the study Central Follow-Up office; maximum follow-up will be 5 years.

2. Prior to Randomization

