[a] Form 11: Quality of Life is only collected at months 6 and 12 and 24 of follow-up., ²Completed by Central Follow-Up Personnel or Chair's Office, ³Completed by a designated adjudication committee

B. Follow-up Procedures

1. Measurement of Outcome Variables

Quality of Life will be measured in-person during baseline observation, and over the phone at months 6, 12 and 24.

Additionally, ICD interrogation records will be reviewed for device-related complications, such as lead failure; the device itself will be interrogated to confirm proper functioning, and to determine if any episodes of ICD therapy have occurred. The results of ICD interrogation will be saved in .PDF format, and transmitted to the study center.

2. Remote Monitoring

In addition to regularly scheduled follow-up, participants randomized to the ICD implantation arm will be monitored where possible using standard device interrogation performed either in association with their follow-up phone calls, or whenever device reports are generated, usually following therapy delivery. All therapeutic activities will be recorded via the device's remote monitoring capabilities, which capture salient physiological data prior to a device-delivered therapy, as well as information about the intervention itself and information about device programming changes. As part of routine clinical practice, these data are transmitted from the device to the manufacturer, placed in a VA-sponsored database accessible to the central follow-up office, and communicated to the treating clinician. The CSP#592 Study Team will access this record in parallel, obtaining either from the device manufacturer or the National Registry; the Study Team's access of the record will not interfere with the treating clinician's ability to receive and act on this information. Data are taken from the device in a completely non-invasive way,

i.e. the participant is uninvolved and unaware of the transmission: no participant contact or interaction is necessary for data exchange.

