In addition to device interrogation during clinic visits participants in the ICD arm will also be followed via remote monitoring where possible, which is now part of the standard of care for ICD patients in the VA system. Participants may be provided with a home monitoring device that can communicate wirelessly with their ICD and will download and transmit a complete interrogation of the ICD on a regular schedule (usually every 6 months). In addition, unscheduled transmissions can be initiated by the ICD if preprogrammed criteria such as lead or battery failure are met. Finally, the participants can initiate a manual transmission if they are instructed to do so by a member of the Study Team, or if they feel like they may be having an issue with their ICD. PDF files documenting all remote transmissions will be forwarded to the national study center and the site investigators by a VA-sponsored device database .

Data obtained from these transmissions will contain PHI including name and SSN. These reports will be protected in the same way as all other case report forms: their access will be granted to Study Team members on a need-to-know basis, and will be stored behind the VA firewall. Besides the Study Team (Chair's Office, Central Follow-Up Office, and WH-CSPCC), a given report will only be viewable by select members of the Events Adjudication Committee (see Section XII. B.). Permission for the Study Team to access this record is granted by the patient in their consent into the study and through registration for the National Database; there is no need for a separate Data Use Agreement with an external agency or manufacturer.

C. Study Withdrawal and Crossover

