Files documenting all in clinic interrogations will be accessed by the Study Team in a separate and independent transaction from that conducted by the care provider as part of routine clinical practice. These files will be used most importantly as source documentation for exploratory analyses of ICD therapy events including the frequency of ICD therapy, the appropriateness of ICD therapy, the rhythms that trigger ICD therapy and the overall number of shocks experienced by participants with ICDs. These files could also be used for other exploratory analyses focusing on other aspects of ICD function. The data contained within these files may be the result of direct interrogation of the device, or a filtered dataset exported from a larger database used in order to increase the efficiency of data analysis.

Lastly, every effort will be made to interrogate the device upon death. This is standard clinical practice and is often impactful in facilitating determination of the cause of death.

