Death due to another cause			

Table 24: Primary Outcome: All-cause Mortality by Treatment Assigned

Primary Outcome (No. of Death)	Treatment 1		Treatment 2		Overall	
	R/N	%	R/N	%	R/N	%
No. of Randomization						
No. of Death (all-cause)						
Hazard Ratio (95% CI)	NA	NA	NA	NA	x.xx	(x.xx, x.xx)

Table 25: Secondary Outcome: Cardiovascular Death by Treatment Assigned

Secondary Outcome (No. of Death)	Treatment 1		Treatment 2		Overall	
	R/N	%	R/N	%	R/N	%
No. of Randomization						
No. of Death (all-cause)						
Hazard Ratio (95% CI)	NA	NA	NA	NA	x.xx	(x.xx, x.xx)

Table 26: QoL MLHF Score by Time Point and Treatment Assigned – All randomized participants

QoL MLHF Score	Treatment 1		Treatment 2		Overall	
	Mean	Std	Mean	Std	Mean	Std
No. of Randomized Participants						
Baseline						
6 Months						
12 Months						
24 Months						

Table 27: Sudden Cardiac Death by Treatment Assigned

Secondary Outcome (No. of Sudden Cardiac Death)	Treatment 1		Treatment 2		Overall	
	R/N	%	R/N	%	R/N	%
No. of Randomization						
No. of Death (all-cause)						
Hazard Ratio (95% CI)	NA	NA	NA	NA	x.xx	(x.xx, x.xx)

Table 28: Summary of ICD reports

	Total	Median (IQR) per participant	Mean (SD) per participant
N Participants yielding at least 1 report		–	–
N Reports			
N Days between implantation and first report			
N Missed Days		–	–
Interval between implantation and 1 st report			
Intervals between reports			
N Reports containing at least 1 therapy		–	–
N Events			
Median (IQR) per subject			
Mean (SD) per subject			
Programming status			
Not changed			
Changed to return to protocol settings			
Changed to accommodate SVT			
Changed to accommodate Syncope			
Changed to accommodate Near-Syncope			
Changed to accommodate Heart Block			
Changed to accommodate Sick Sinus			
Changed for unknown reasons			
Changed for other reason			
TOTAL Programming Status Change			

Table 29: ICD Therapy Event Frequency Table

N Participants randomized to ICD				
N Participants yielding at least one report				
N Events				
	Number of participants with at least 1 event	Per-cent	Total Number of events	Per-cent
ATP Pacing Events				
No Change				
Acceleration without termination				
Acceleration, termination into additional therapy				
Termination, with tachycardia restart into additional therapy				
Termination				
NA				
Unknown				
TOTAL				
Shock Events				
No Change				
Acceleration without termination				
Acceleration, termination into additional therapy				

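### SAP 2.2.8 ends shock-free time at the last follow-up, not the last device read, so unread device time counts as shock-free; the shock-mortality model has no rule for shock status after the last read

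*Combined protocol and SAP*

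**What the plan says.** SAP 2.2.8 (Device Data) plans three time-to-event analyses of ICD shocks.

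- **Time to first shock, Kaplan-Meier with log-rank.** No censoring rule is stated.
- **Time to first inappropriate shock, Cox model, among patients with an active ICD.** Here "subjects who never experience a shock or experience only appropriate shocks will be censored at the last time of follow-up".
- **Shock and mortality, a separate Cox model,** "where time to death will serve as dependent variable and inappropriate shocks, appropriate shocks and other related clinical variables will be" entered as time-dependent covariates. Nothing is said about a participant's shock status after the last device read.

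On where shock data come from, SAP 2.2.8 says: "The device data will be collected during study follow-up visits for participants in the ICD arm and followed by remote monitoring where possible". Protocol III.C.1 makes the study contacts telephone calls ("Study follow-up phone calls will be scheduled for months" 1 to 4, then every 6 months). Protocol XI.B.2 has the ICD arm "monitored where possible using standard device interrogation performed either in association with their follow-up phone calls" or whenever device reports are generated, and says a home monitor may be provided. Routine remote transmission is described as usually 3-monthly in Protocol VI.C and SAP 1.3.2.5, but usually 6-monthly in Protocol XI.B.2.

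On death, SAP 1.3.2.5 says "every effort will be made to interrogate the device upon death"; Protocol XII.J qualifies this as where feasible.

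The report shells expect gaps. SAP Table 28 has a row for missed days. Tables 29 to 31 list "N Participants yielding at least one report" separately from the number randomized to ICD, without naming the percentage denominator. No analysis rule uses these counts.

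**The concern.** A shock can be known only from an interrogation or a transmission. A participant can be in study follow-up, reachable by telephone or known to be alive, long after the device was last read. If shock-free time runs to the end of follow-up, the unread stretch adds to the denominator of the shock rate while any shock in it is missing from the numerator. First-shock rates and cumulative incidence come out too low, and the Cox model treats poorly monitored participants as shock-free.

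The mortality model has a different weakness. Deaths can be captured from the Vital Status File or public records after device data have stopped (Protocol XI.C; SAP 2.2.3), so shock status can be unknown for part of the time at risk. Because interrogation is specially sought at death, late shocks may be found more often in those who die than in those who live. Ascertainment of the exposure then depends on the outcome.

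At stake are the device analyses that SAP 2.2.8 singles out, including risk of death after shock, and the publication in Protocol Table 20 comparing survival with OMT, ICD without shocks and ICD with shocks.

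**Working it through.** The plan states no shock rate, unread fraction or shock-mortality effect, so there is no figure of its own to reproduce. The check is a simulation of direction and plausible size, with 300,000 ICD participants per scenario.

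**Inputs from the documents**
- Control mortality 15% per year and hazard ratio 0.75 (SAP 2.1). ICD-arm death hazard = 0.75 × −ln(1 − 0.15) = 0.75 × 0.1625 = 0.122 per year.
- Follow-up uniform over 2 to 5 years (SAP 2.1).
- Reads every 3 or 6 months (both intervals are stated).
- The device stores therapy events (SAP 1.3.2.5), so a later read recovers earlier shocks.

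**Assumptions**
- One shock type, true first-shock rate 5 per 100 person-years (2 and 10 also run).
- True shock-mortality HR 1, 2 or 3.
- Monitoring lapses at a random time in 0, 20 or 40% of participants.
- 0, 50 or 100% of deaths are interrogated.
- Monitored survivors are read at exit.

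**Quantities**
- Rate under the SAP rule = recorded first shocks ÷ person-time to first recorded shock or last follow-up.
- Rate under the alternative = the same shocks ÷ person-time to first recorded shock or last read.
- Mortality HR = one-covariate time-dependent Cox model using recorded shocks.

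**Results for 6-monthly reads and true HR 2** (rates per 100 person-years)

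| Lapse | Deaths read | Time unread | True rate | SAP rule | Last-read rule | HR, all shocks known | HR, recorded shocks |
|---|---|---|---|---|---|---|---|
| 0% | 0% | 3.2% | 4.97 | 4.68 | 4.83 | 2.02 | 1.66 |
| 0% | 100% | 0% | 5.01 | 5.01 | 5.01 | 2.01 | 2.01 |
| 20% | 0% | 10.6% | 4.98 | 4.32 | 4.84 | 2.00 | 1.64 |
| 20% | 100% | 6.4% | 4.98 | 4.69 | 5.02 | 1.99 | 2.09 |
| 40% | 0% | 18.0% | 5.04 | 4.02 | 4.92 | 1.99 | 1.64 |
| 40% | 50% | 15.4% | 5.07 | 4.25 | 5.03 | 2.03 | 1.95 |
| 40% | 100% | 12.7% | 4.96 | 4.40 | 5.06 | 2.00 | 2.21 |

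**Shock rate.** At 40% lapse with no reads at death, the SAP rule gives 4.02 against 5.04: 1 − 4.02/5.04 = 20% too low. The largest loss in the set is at true HR 3 with the same reading pattern: 1 − 3.84/4.97 = 23%. With every death read and no lapse the loss is nil. Across the scenarios at 5 per 100 person-years, the SAP rule gives 3.84 to about 5.0 and the last-read rule 4.69 to 5.17. The last-read rule is much closer but not exact, because reads prompted by death make its censoring partly informative.

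**Mortality association.** Two mechanisms oppose each other. A shock between the last read and death goes unrecorded if the device is not read at death, so a post-shock death falls in the unshocked group and the HR drops. If deaths are read but lapsed survivors are not, shocks are recovered preferentially in the dead and the HR rises.

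- No deaths read: HR 1 becomes 0.85 to 0.92, HR 2 becomes 1.64 to 1.83, HR 3 becomes 2.37 to 2.67.
- Half of deaths read: HR 2 becomes 1.83 to 2.00.
- All deaths read, 20 to 40% lapsed: HR 1 becomes 1.06 to 1.12, HR 2 becomes 2.08 to 2.21, HR 3 becomes 3.08 to 3.32.

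**The case against.** The strongest reply is that the rule need not be read so literally. The sentence sits in the Device Data section, which says device data are collected at study follow-up. Form 14 (ICD Follow-Up) is scheduled at the initial follow-up and every 6 months. Protocol XI.B.1 says the device will be interrogated to see whether therapy occurred. In-clinic files are also obtained, and failure to register for remote monitoring within 30 days of implantation is a protocol deviation. Because the device stores its events, an intermediate gap closes at the next read. The gap between participants randomized to ICD and those with a report also includes people never implanted, whom the active-ICD restriction already removes.

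Most of this stands, and it limits the problem mainly to time after the last read and to implanted participants never read. It does not remove the problem: the same protocol section makes monitoring conditional on feasibility, the shells count missed days, and the rule names follow-up rather than a read. If reads always occur, the proposed wording changes nothing.

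Three stronger readings are tempting, and the documents do not support them.

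- **That the last follow-up is a telephone call without a read.** This is an inference; interrogation may accompany the calls.
- **That the shock-mortality association is biased upward.** This needs deaths to be read far more completely than survivors, and the documents give neither proportion.
- **That shock rates could be about a third too low.** If 10, 20 or 30% of participants are never read in life or at death, the first-shock rate is 11, 21 or 32% too low. That pattern disregards in-clinic reads and later recovery from device memory, so it is not a basis for the expected size.

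**Conclusion.** The point holds for the time-to-shock analyses. Taken as written, the rule counts unread device time as shock-free and can only lower first-shock rates. The loss is nil to about 23% relative in the lapse scenarios; its actual size is unknown because it rests on assumed lapse and death-read proportions.

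The censoring sentence does not govern the shock-mortality model. There the gap is the missing rule for shock status after the last read, combined with reads sought at death. The possible bias has no fixed sign, which is itself a reason to settle the rule in advance.

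These analyses are exploratory and confined to the ICD arm. The primary all-cause mortality comparison does not use device data and is unaffected.

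**What to change.** Amend SAP 2.2.8 and the table shells.

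1. **Kaplan-Meier and Cox time-to-shock analyses.** End shock-free time at the last interrogation or transmission covering the period, whether scheduled, in-clinic or remote. Implanted participants with no read contribute no shock-free time.
2. **Table 29.** Use participants with at least one report as the percentage denominator, and keep the number randomized to ICD as a printed count.
3. **Shock-mortality model.** Keep all deaths. State how shock status is set after the last read. Add a sensitivity analysis leaving out shocks found only at post-mortem interrogation. Do not restrict this model to device-covered person-time: that would drop every death without a post-mortem read.
4. **Check on triggered reports.** Some transmissions are prompted by therapy, so ending time at the last report can select toward shocks. Repeat the time-to-shock analyses using scheduled reads only.
5. **Transmission interval.** Reconcile the 3-month and 6-month statements, so that expected and missed reads can be counted on one basis.

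The cost is wording and modest programming; Table 28 already calls for report intervals and missed days. Some person-time is lost and intervals are wider, by an amount that depends on the unread fraction.
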